Neuroimaging Component. Given the severe negative outcomes associated with co-occurring PTSD and AUD, investigating potential neural circuitry underlying PTSD/SUD as well as neural circuitry involved in positive therapeutic response to doxazosin could be important in guiding future studies targeting this circuitry using other therapeutic agents or treatment modalities. To that end, fMRI data will be acquired at baseline and end-of-treatment on all eligible participants to examine (a) resting state connectivity, and (b) response to trauma, substance, and neutral cues. We will continue to work closely with the CAP Co-Is and Neuroimaging Core, directed by [name], to ensure comparability of imaging data acquisition and pre-processing. Scans will be conducted at the MUSC Center for Biomedical Imaging (CBI), which houses a Siemens 3T TIM Trio MRI scanner (Siemens Medical, Erlangen, Germany). The neuroimaging component will involve three visits, each lasting 60-90 minutes and following the same procedures. In visit 1, imagery scripts will be developed according to standardized procedures described by Sinha (Sinha & Li, 2007) and employed in our ongoing research with Veterans. During visits 2 and 3 (see Fig 5), participants will first be screened for metal using a handheld metal detector. Trained staff will position subjects on the scanner bed with foam padding placed around their head to prevent motion. Participants will wear headphones to listen to the audio-recorded scripts. For co-registration and normalization of functional images, a high resolution T1-weighted MPRAGE anatomical image will be acquired with the following parameters: TR = 2100 ms, TE = 4.18 ms, flip angle = 12°, field of view = 256 mm, slice thickness 1.0 mm. The scanning planes will be oriented parallel to the anterior commissure-posterior commissure line. Next, participants will be asked to relax and keep their eyes opened and fixed on a cross-hair for six-minutes while resting state data are collected.

Following the resting state scan, participants will be exposed to trauma, substance and neutral cues. Resting state scans will always occur before trauma and substance cue runs (Fig. 5). We will use a block design

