fMRI Analysis: Functional connectivity will be measured using a PPI seed-based approach [2]. PPI analyses for resting state, trauma and substance cues will be performed separately. Customized sq. wave forms representing the trauma run (1=trauma block and -1=neutral block) and the substance cue run (1=substance block and -1=neutral block) the duration of each block will be convolved with a double-gamma hemodynamic response function. A mask of the seed region will be made using a 12-mm diameter sphere located in the center

of the amygdala using the MNI coordinates (x, y, z = ±22, 0, -22). The transformation parameters described above will also be applied to the mask. For each subject, the mean corrected and high pass filtered time series of the BOLD signal in the AMY will be extracted and used in a single subject whole brain PPI analysis. The PPI model will include the task vector, time series of the BOLD signal in the AMY, a term representing the positive task x seed interaction, and a term representing the negative task x seed interaction. The first level analysis will generate contrast images of the parameter estimates for each of the four regressors. Voxels will be thresholded at $Z>2.3$ using a corrected cluster threshold of $p=0.05$. The contrast images of the parameter estimates of the positive and negative task x seed interactions will be combined for group-level t-tests to identify regions that exhibited altered connectivity with the AMY during the trauma and substance cues as compared to neutral cues. All group-level results will be thresholded at $Z>2.3$ using a corrected cluster threshold of $p=0.05$. Separate linear regression tests will be used to test for associations between PFC-AMY connectivity at baseline and improvement in PTSD and SUD symptoms during treatment. Changes in CAPS-5 total scores will be regressed against the parameter estimate obtained from the center voxel from each cluster that exhibited a significant task x seed interaction with the AMY at rest and in response to the trauma cue (Hypothesis 3A). The number of days to first use (TLFB) will be regressed against the parameter estimate obtained from the center voxel from each cluster that exhibited a significant task x seed interaction with the AMY at rest and in response to the substance cues (Hypothesis 3B).

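### The resting-state predictor for Hypotheses 3A and 3B is a task-by-seed interaction that cannot be estimated in a scan with no task; as a minor addition, the 3B days-to-first-use regression has no time origin or rule for participants with no observed use

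*Combined protocol and SAP*

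**What the plan says.** **Rest.** The Neuroimaging Component section describes the resting scan as a separate acquisition before any cue run: "participants will be asked to relax and keep their eyes opened and fixed on a cross-hair for six-minutes while resting state data are collected". The fMRI Analysis section measures connectivity by psychophysiological interaction (PPI) from an amygdala seed and states that "PPI analyses for resting state, trauma and substance cues will be performed separately". Its waveforms are those "representing the trauma run (1=trauma block and -1=neutral block) and the substance cue run (1=substance block and -1=neutral block"; none is given for rest. The model contains the task vector, the seed time series, "a term representing the positive task x seed interaction, and a term representing the negative task x seed interaction". Group-level t-tests on the interaction images then "identify regions that exhibited altered connectivity with the AMY during the trauma and substance cues as compared to neutral cues". For 3A, the change in CAPS-5 is regressed on the estimate from clusters that "exhibited a significant task x seed interaction with the AMY at rest and in response to the trauma cue". For 3B the clusters are those that "exhibited a significant task x seed interaction with the AMY at rest and in response to the substance cues".

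**Days to first use.** Hypothesis 3B is worded as prediction of the time to first alcohol or drug use. The fMRI Analysis section specifies linear regression: "The number of days to first use (TLFB) will be regressed against the parameter estimate obtained from the center voxel from each cluster". The sentence introducing both regressions refers to improvement during treatment, which suggests a 12-week window but does not tie it to this variable. The TLFB entry under Assessment Instruments covers the 60 days before the study, treatment and follow-up. The Missing Data section gives a general imputation rule for more than 10% missing data and does not mention this endpoint.

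**The concern.** An interaction between task and seed needs a task that varies within the scan. The resting scan has none, yet resting connectivity is half of each imaging hypothesis. If the specified quantity does not exist, the analyst must substitute another measure and find a location for it. Nothing in the text prevents that choice from being made with the outcomes in view, in an analysis of 44 participants.

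The 3B outcome has a smaller gap. A participant who never uses during observation has no number of days to first use. Whether that person is dropped, set to the last day or treated as censored changes both the slope and the power, and the plan does not say which applies. It also does not say from which day the count begins.

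**Working it through.** **1. The plan's own figure.** The Power section gives 34 participants in total for 80% power at d = 1.0, two-tailed alpha .05, for relapsers against non-relapsers. A two-sample t-test with the noncentral t distribution gives 17 per group, 34 in total, with power 0.807. The figure reproduces and is not in dispute.

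**2. Can the resting interaction be estimated?** The columns are an intercept plus the plan's four regressors: task, seed, positive task x seed and negative task x seed. In a scan without a task, the task vector is a constant c. Then
- task = c × intercept (or zero);
- each interaction = ±c × seed (or zero).

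Only two independent columns remain. Numerically, with 180 volumes (6 min at the 2 s TR given for the functional images) and c = 0, +1 or −1, the rank is 2 of 5 each time. The result does not depend on the number of volumes.

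**3. Is the cue run affected?** With 360 volumes (12 min at 2 s) and an assumed 60 s block length, the rank depends on how the two interaction terms are coded, which the plan does not state:
- negative term equal to minus the positive term: rank 4 of 5, so one interaction contrast is estimable;
- cue and neutral blocks convolved separately and each multiplied by the seed: rank 5 of 5.

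Either way the cue interaction is estimable, so the defect is confined to rest.

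**4. Is there another route to a resting cluster?** The group t-tests that locate clusters contrast only trauma or substance cues with neutral cues. No step locates a cluster at rest.

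**5. Size of the 3B gap (illustrative).** Assumptions: N = 44, exponential first-use times, log-hazard linear in a normal predictor, an 84-day window, two-sided 0.05 and 20,000 simulated trials per cell. The documents give no never-use share, so 5, 10, 23 and 32% are assumed. The last two equal the doxazosin abstinence rates for weeks 9–12 in the Power section. Never using through week 12 is a stricter condition, so under those rates they are ceilings: 44 × 0.23 ≈ 10 and 44 × 0.32 ≈ 14 participants. With 24 of 45 relapsing, as in the study cited under Power, a hazard ratio of 2.14 per SD corresponds to d = 1.00, and 1.6 to d = 0.65.

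| Power at never-use 5/10/23/32% | HR 1.6 per SD | HR 2.14 per SD |
|---|---|---|
| Linear, never-users set to last day | 0.77/0.76/0.69/0.64 | 0.98/0.98/0.97/0.95 |
| Cox | 0.79/0.78/0.73/0.69 | 0.99/0.99/0.98/0.97 |
| Linear, never-users deleted | 0.55/0.41/0.21/0.14 | 0.91/0.81/0.50/0.33 |
| Last day, 30% leaving early | 0.70/0.65/0.55/0.48 | 0.96/0.95/0.90/0.84 |
| Cox, 30% leaving early | 0.76/0.74/0.68/0.63 | 0.98/0.98/0.97/0.95 |

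Without dropout, Cox gains 2 to 5 points over last-day coding at HR 1.6 and 1 to 2 points at HR 2.14. A repeat simulation put the top of the range at about 7, so 1 to 7 is the safe statement. With an assumed 30% leaving early, the gain is 6 to 16 points at HR 1.6 and 2 to 11 at HR 2.14. The dropout rows matter only if the 44 include early leavers. The Power section leaves this unclear, since it describes the imaging group first as volunteers and then as completers.

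**The case against.** **On rest.** The interaction wording was probably carried over from the cue runs. The hypotheses speak of connectivity at rest, the method is described as seed-based, and the first-level model produces an image for each of its four regressors, one of which is the seed. So the right quantity is already an output. This stands, and it makes the repair easy. It does not remove the error: the text says a PPI analysis is done for rest, takes the predictor from an interaction for both hypotheses, and nowhere names the seed coefficient or where to read it. A reader might infer that the choice will be made after the data are seen. The documents support only that it could be, since a wording change before analysis would close the gap. A reader might also infer that 3A and 3B cannot be tested at all, but their cue-run halves can.

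**On 3B.** At the plan's own effect size, last-day linear regression already has power of 0.95 to 0.98 without dropout, so a censored-data model adds little. This stands. The deletion row in the table invites a stronger reading, that 3B will lose most of its power. No section says never-users are deleted. The intent-to-treat sentence under General weighs against it, although the Power section's restriction of 3A and 3B to the imaging subset means that sentence does not fully settle the matter. The highest never-use shares are also ceilings, and entry requires a current substance use disorder but no abstinence, so early first use is plausible.

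**Conclusion.** The resting part is wrong as written: the interaction is not estimable (rank 2 of 5 for any constant task vector), and no resting cluster can be selected. This follows from the design alone and needs no assumption about effects or block timing. It should be corrected before the imaging data are analysed.

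The 3B part is a minor, cheap improvement. The size depends on the assumed never-use shares, exponential times and hazard ratios: about 1 to 7 points of power over last-day coding without dropout, and about 2 to 16 points with an assumed 30% leaving early. Larger losses would need deletion of never-users, which the plan does not state.

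The Problems and Alternative Strategies section makes neuroimaging a secondary objective. Hypotheses 1 and 2 are not affected.

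**What to change.** 1. **Rest.** Replace the task-by-seed interaction with the amygdala-seed coefficient, or a Fisher-z correlation. Fix the location before analysis in one of two ways: a pre-specified PFC region, or clusters within PFC from a group map of the seed coefficient at the plan's existing threshold. Keep PPI for the cue runs.
2. **3B.** Use Cox regression or another censored-data model from a stated day 0. Censor observed abstainers and early leavers at their last TLFB-observed day within a stated window, which could end at week 12 or run through the follow-up that TLFB already covers. State that these participants are censored and are not imputed under the Missing Data rule.

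The cost is SAP wording and standard software, with no new data, scans or visits. The downside is that the location, origin and window must be settled before analysis.

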1. RISKS TO SUBJECTS

Drs. [name], [name], [name], [name], [name] and [name] have all completed the University of Miami computer-based CITI Human Subjects Research Education Course. The research team includes two licensed clinical psychologists (Drs. [name], PI and [name], Co-I) and two board certified psychiatrists (Co-Is, Drs. [name] and [name]) with extensive clinical research experience in posttraumatic stress disorder (PTSD) and substance use disorders. [name] (Co-I) also has clinical research experience in posttraumatic stress disorder (PTSD), alcohol use disorders (AUD), and neuroimaging. [name] has expertise in neuroimaging. All research activity, informed consents and continuing reviews will be reviewed by the Medical University of South Carolina (MUSC) Institutional Review Board (IRB) and the Ralph H. Johnson VAMC Office of Research

and Development (R&D) committee, in compliance with 45CFR46 before the research is initiated. Continuing review will occur annually.

Human Subjects Involvement and Characteristics

A total of 144 adults will be recruited over a 4-year period. The inclusion/exclusion criteria are as follows:

Inclusion Criteria:

1. Male or female; any race or ethnicity.
2. Served in U.S. Military – any branch or operation.
3. Subjects must be able to comprehend English.
4. Meet criteria for current (i.e., last 6 months) Substance Use Disorder (SUD) using a modified version of the MINI 7.0 (i.e., must meet DSM-5 criteria for SUD in the past 6 months instead of 12 months).
5. Meet DSM-5 criteria for current (i.e., last month) PTSD.
6. Subjects taking psychotropic medications will be required to be maintained on a stable dose for at least four weeks before treatment initiation. This is because initiation or change of medications during the course of the trial may interfere with interpretation of results.
7. Must consent to random assignment to doxazosin or placebo.
8. Must consent to complete all treatment and follow-up visits.

Exclusion Criteria:

1. Subjects meeting DSM-5 criteria for current bipolar affective disorders, as the study protocol may be therapeutically insufficient.
2. Subjects experiencing significant withdrawal symptoms, as evidence by a score of 10 or above on the Clinical Institute Withdrawal Assessment of Alcohol (CIWA). These subject will be referred for clinical detoxification and may be re-assessed for study eligibility after medically supervised detoxification has been completed.
3. Individuals considered an immediate suicide risk or who are likely to require hospitalization during the course of the study.
4. Previous treatment with doxazosin.
5. Subjects on maintenance anxiolytic, antidepressant, or mood stabilizing medications which have been initiated during the past four weeks. If it is determined, based on clinical criteria, that a subject needs to be started on maintenance medications for anxiety, mood or psychotic symptoms during the course of the study, they may be discontinued from the treatment trial.
6. Women who are pregnant, nursing or not practicing an effective form of birth control.
7. Individuals with a history of or current medical illness including unstable angina, myocardial infarction, congestive heart failure or other cardiac condition, hypotension, renal or hepatic disorders, endocrine disorders, prostate or other cancer, pancreatitis, or a seizure disorder.
8. Subjects with abnormal liver function test (LFTs) as evidenced by laboratory findings of SGOT or SGPT greater than two times normal.
9. Subjects with a history of adverse reactions to quinazolines or other alpha-1-antagonists (such as allergic reactions, priapism, hepatitis, angioedema, or intraoperative floppy iris syndrome).
10. Individuals currently taking alpha blockers (terazosin, prazosin), hypnotics/benzodiazepines, atypical antipsychotics (olanzapine, quetiapine, risperidone, clozapine), alpha-2-agonists (Clonidine, methyldopa, tizanidine, guanfacine), conivaptan, boceprevir, idelalisib, PDE-5 inhibitors or alpha-1-antagonists, protease inhibitors (treatment of HIV), oral antifungals, alfuzosin, pazopanib, silodosin, tadalafil, or tamulosin.
11. MRI exclusions: Claustrophobia; tattoos above the shoulders after evaluation by MRI technician; permanent eyeliner or permanent artificial eyebrows; cardiac pacemaker; metal fragments in eye, skin, or body, including shrapnel; heart valve replacement; brain clips; venous umbrella; being a sheet-metal worker or welder; lifetime history of aneurysm surgery; intracranial bypass, renal, or aortic clips; prosthetic

devices such as middle ear, eye, joint, or penile implants; joint replacements; non-removable hearing aid, neurostimulator, or insulin pump; shunts/stents; metal mesh/coil implants; metal plate/pin/screws/wires; or any other metal implants.

No special classes of subjects, such as, pregnant women, prisoners, institutionalized individuals, or others will be recruited for this study.

Potential Risks

Some participants may experience distress by questions pertaining to their substance use history, trauma or their emotional functioning. All participants will be informed at the outset that the study is voluntary and they may terminate participation at any point. Our past and ongoing research suggests that data collection using many of these measures can be conducted without undue psychological distress or exacerbation of symptoms. This experience includes substantial research with younger and older adults, active duty service members, OEF/OIF/OND military Veterans, rape victims, victims of other forms of violence (e.g., natural disasters, car accidents), and work on large-scale studies asking questions about similar topics with general population samples. Legal risks arise if individuals are homicidal or suicidal and make these intentions known to project staff, who may then be required to notify authorities and the target of homicidal intent. These risks are outlined in the informed consent documents.

In the event that subjects experience psychological distress secondary to participation, they will be encouraged to telephone the Principal Investigator (PI), [name], who is a licensed clinical psychologist. They will be given [name] contact information at the time of consent, as well as resources for local and national 24-hour hotline numbers. In addition, participants will have access to urgent care services at the VAMC. The research team is comprised of licensed clinical psychologists and psychiatrists with extensive experience working with adults who have experienced significant life stressors and drug/alcohol addiction. If assessors or project staff believe that a participant is significantly distressed by participation, the PI will be notified and will contact the participant immediately to assess distress and assure participant safety. If called by a participant, the PI will attempt to address all participant concerns and will set up an alternate referral for clinical services outside the project if desired.

If eligible, participants may be asked to complete two neuroimaging scans (functional magnetic resonance imaging; fMRI), which will be conducted at the MUSC Center for Biomedical Imaging (CBI), which is located at [name] on the MUSC campus (within 2 blocks of the VA). There are very few potential risks from fMRI itself. There is no exposure to ionizing radiation and the machine and scanning sequences and gradients are approved by the Food and Drug Administration (FDA) for routine clinical use. Individuals who are claustrophobic may experience some anxiety during the scanning procedures. A patient may experience some loud noises during the scanning procedure and there is a mild risk of hearing damage if patients are not given hearing protection. All participants in the study will be given hearing protection. Participants may experience psychological discomfort from undergoing the scanning procedure, such as boredom and fatigue. Ferrous objects in the body that are undetected could move during scans. This could lead to tissue damage and hemorrhage. These risks are outlined in the informed consent document. In our past and ongoing studies utilizing fMRI, we have been able to safely complete imaging procedures without undue distress or negative outcomes. This includes research with military Veterans who have current PTSD and co-occurring substance use disorders.

All medications have potential side effects. Side effects that have occurred in clinical trials with doxazosin include dizziness/fainting, fatigue, headache, shortness of breath, diarrhea, abdominal pain, edema, priapism, and hypotension. Doxazosin can cause floppy iris syndrome during cataract surgery. Participants will be informed of all potential side effects associated with doxazosin and closely monitored each week.

Because participants are U.S. military personnel, absolute confidentiality of research records cannot be guaranteed. We will, however, make all possible efforts to protect the privacy and confidentiality of study participants. Participants will be provided with a written informed consent document which specifies the risks and confidentiality protections and limits of study procedures.

Sources of Materials

Data will be in the form of structured clinical interviews conducted by trained Independent Evaluators, self-reported questionnaires, medical record review, urine and breath samples, and neuroimaging data that will be obtained specifically for research purposes.

In addition to consenting for this study, participants will be offered participation in the STRONG STAR Repository. The South Texas Research Organizational Network Guiding Studies on Trauma and Resilience, or STRONG STAR, is a multidisciplinary and multi-institutional research consortium funded by the U.S. Departments of Defense (DOD) and Veterans Affairs (VA) to develop and evaluate the most effective early interventions possible for the detection, prevention, diagnosis, and treatment of combat-related PTSD and related conditions in active-duty military personnel and recently discharged Veterans. Under the leadership of the UTHSCSA and based in south-central Texas, STRONG STAR brings together the expertise of a world-class team of military, civilian and VA institutions and investigators and one of the largest populations of active-duty and recently discharged OEF/OIF/OND Veterans in the nation.

The STRONG STAR Repository is approved by the UTHSCSA IRB, which also reviews research for the STVHCS, and has received Central VA approval as a tissue bank maintained at the UTHSCSA. The STRONG STAR Repository is a large comprehensive database of information, biological specimens and neuroimages related to the identification, assessment, and treatment of PTSD and related conditions in our active duty and retired veterans of combat operations. All information entered into the Repository will be extracted from primary datasets collected as part of IRB-approved studies, including this study, being conducted and /or supported by the projects of the CAP. A unique, sequential alpha-numeric ID is assigned to each participant at the time of recruitment into this study. However, all repository data will be identified with a different code number that can be cross linked to the original study code only through records maintained by the Data Management and Biostatistics Core. Data, biological specimens and images constitute the STRONG STAR PTSD Repository. Participation in the repository is completely voluntary and entirely optional which means that a potential participant's willingness to participate in the repository has no influence upon their eligibility to participate in the primary study they have either already enrolled in or are considering enrolling in. At the conclusion of this study, participants who signed the consent to have their specimens and data placed in the STRONG STAR Repository will be maintained under the IRB-approved Repository protocol. Biological specimens and information from study participants who declined participation in the STRONG STAR Repository will be permanently de-identified (i. e., all PHI will be deleted from the study data bases) and the de-identified blood and information placed in the Repository for future use.

